12.2 Statistical Analyses

12.2.1 Interim Analysis

Details of all planned statistical analyses including the interim analyses will be provided in the study SAP. In summary, four interim analyses for futility and overwhelming efficacy are planned. These analyses will use the error-spending function method with stopping guidelines that are similar to the O'Brien and Fleming (OBF) type stopping boundaries. The proposed timelines can be altered based on the input from the DSMB. The SDMC will conduct these analyses and compile the reports for the DSMB.

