12.2.3 Primary Efficacy Analysis

The primary outcome analysis of the 90-day mRS will use a stratified dichotomy methodology for assessing improvement as defined in the Primary Outcome section above. Outcome differences will be analyzed under the intention-to-treat principle, therefore all randomized subjects will be included in the primary analysis sample. To assess efficacy, the treatment groups will be compared with respect to the proportion with favorable outcome 90 days post randomization after controlling for the prognostic variables included in the randomization scheme. A Wald chi-square test will be performed to compare the treatment group proportions using a two-tailed significance level of 0.05. Adjusted relative risks will be reported with two-sided 95% confidence intervals.

Additional analyses will identify potential confounding (prognostic) variables to be used as covariates in subsequent secondary analyses of the primary outcome using generalized linear modeling techniques. Specific covariates include age, gender, race, ethnicity, admission blood glucose, previous stroke, time between stroke onset and treatment and lacunar subtype. If statistically significant differences are evident, post-hoc analyses will be conducted to determine if differences had an effect on the conclusions from the pre-specified primary analysis.

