4.2 Sample Size Re-estimation Plan

We recognize that sample size estimation is based on assumptions and if the control success rate is higher than 25% then we may begin to see a decrease in power. For example, if the control rate is as high as 30%, the power drops from approximately 80% to 77% to detect a 7% absolute difference if one truly exists. To reduce the likelihood of an underpowered study due to an incorrect overall event rate assumption, we propose to conduct a sample size re-estimation prior to the 1st interim efficacy/futility analysis (i.e., once 500 consecutively randomized subjects complete the 90-day mRS). The overall success rate of the population will be estimated using the interim data for the sole purpose of sample size re-estimation (not for interim testing of a treatment effect). Combining sample size re-estimation with the proposed group sequential design (GSD) will improve two aspects of the design – misspecification of the overall event rate (N-reestimation) and misspecification of the treatment effect (GSD) – while preserving the overall type I error rate. In addition, the GSD will help protect from unnecessarily continuing the trial even if the re-estimation suggests a larger overall sample size.

Following the approach of Gould and Shih⁵, sample size adjustment will be based on the observed overall event rate assuming a 7% absolute difference between treatment arms (the value specified under the alternative hypothesis). If the observed overall event rate is greater than the assumed, then we may require additional observations. The below table provides various hypothetical scenarios of the observed event rate and the required additional observations to maintain 80% power.

Observed Overall Event Rate	Estimated Control Rate (assuming 7% difference)	Power if No N-Adjustment	Additional Total N Required to Maintain Power at Final Analysis	N for 1 st interim analysis	Delay of 1st interim look (months)*
0.265	0.23	82%	-	500	0
0.285	0.25	81%	-	500	0
0.305	0.27	79%	58	522	<1
0.325	0.29	78%	108	540	1-2
0.345	0.31	77%	154	554	1-2
0.365	0.33	76%	194	570	2-3
0.385	0.35	75%	228	582	2-3

*assuming accrual rate of 33.3 patients per month

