10.1.2 Primary Efficacy Analysis at the End of the Trial

The primary outcome analysis of the 90-day mRS will use a stratified dichotomy methodology for assessing improvement as defined in the Primary Outcome section above. Outcome differences will be analyzed under the intention-to-treat principle, therefore all randomized subjects will be included in the primary analysis sample. To assess efficacy, the treatment groups will be compared with respect to the proportion with favorable outcome 90 days post randomization after controlling for the variables included in the randomization scheme. The primary statistical analysis will develop a generalized linear model using the PROC GENMOD procedure in SAS® v9 with treatment group as the factor of interest and baseline NIHSS strata (3-7, 8-14, 15-22) and thrombolysis use (Yes/No; includes both IV and IA therapies) as covariates. A Wald

[figure not shown]
chi-square test will be performed to compare the treatment group proportions using a two-tailed significance level of 0.05. Adjusted relative risks will be reported with two-sided 95% confidence intervals. Additional analyses will identify potential confounding (prognostic) variables to be used as covariates in subsequent secondary analyses of the primary outcome. Specific covariates include age, gender, race, ethnicity, admission blood glucose, previous stroke, lacunar subtype, and time between stroke onset and treatment. If statistically significant differences are evident, then post-hoc analyses will be conducted to determine if differences had an effect on the conclusions from the pre-specified primary analysis.

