10.1.3 Interim Analysis Plan

The study is designed using four interim looks for both efficacy and futility of the primary outcome and one final look for a total of 5 planned analyses of the primary outcome. The interim analysis plan uses the error spending function method with O'Brien and Fleming (OBF) type stopping guidelines⁷⁻⁹. The error spending function distributes the type I and II error rates across the interim monitoring points giving the flexibility of changing the intervals of monitoring while still preserving the overall type I and II error rates. The OBF-type boundary is considered conservative as its boundaries make it difficult to terminate a study early on by requiring extreme early evidence of efficacy or futility. It spends smaller amounts of alpha at the first look and gradually increases the spending as more information is acquired. The trial may be stopped for overwhelming efficacy of one treatment group over the other or for futility at the planned interim analyses if the test statistic crosses the respective boundaries.

The current plan is to conduct the first interim analysis after approximately 500 randomized subjects complete the primary outcome assessment (90-day mRS). Assuming an accrual rate of 33.3 patients per month, it is anticipated that the 1st look will occur roughly 2.5yrs from the start of enrollment. Subsequent analyses will occur after every additional 200 subjects complete the 90-day mRS (i.e., 700, 900, and 1100). The interval may be altered if requested by the DSMB. The stopping boundaries are defined using the gamma family spending functions with a gamma value of -4 (closely resembles OBF boundaries)¹⁰. Specific to the futility boundaries, they are derived as non-binding meaning that if a futility boundary is crossed there is the ability for it to be overruled without inflation of the type 1 error rate. If the crossing of an efficacy boundary is overruled, then this decision can impact the type II error rate but not the type I error rate. EAST[®] 5 software (Cytel Corporation) was used for the boundary calculations.

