The below graph depicts the stopping boundaries based on the test statistic at each planned look. The inner wedge represents rejection of the alternative (futility) and the outer boundaries represent rejection of the null (overwhelming efficacy). The boundaries have the property that under the null hypothesis of no difference the overall probability of crossing either outer boundary does not exceed the overall type I error rate and under the alternative hypothesis the overall probability of crossing the inner boundary does not exceed the type II error rate. Appendix A provides further details on the properties of the stopping boundaries.

The following table lists the test statistics (shown in the above graph) and the corresponding p value as well as the probability of crossing either of the boundaries (futility or efficacy) at a particular look. Using the 5th column as an example, under the null hypothesis of no difference, the probability of crossing the specified boundary for either efficacy or futility is 0.05 at the 1st look, 0.10 for the 2nd look and so forth. Overall the probability of stopping the study (for futility) by the 4th look is 0.75 under the null and 0.66 under the alternative (stopping for efficacy).

Analysis	Approximate Sample Size	Minimum Test Statistic Z value (p value) to reject H ₀	Minimum Test Statistic Z value (p value) to reject H _a	Boundary Crossing Probabilities Under H ₀	Boundary Crossing Probabilities Under H ₁
1	500	2.97 (0.003)	0.06 (0.949)	0.05	0.12
2	700	2.86 (0.004)	0.13 (0.896)	0.10	0.13
3	900	2.65 (0.008)	0.45 (0.652)	0.27	0.19
4	1100	2.42 (0.016)	1.05 (0.293)	0.33	0.22
Final	1400	2.02 (0.043)	2.02 (0.043)	0.25	0.34

The SDMC will be responsible for conducting these analyses and compiling the reports for the DSMB. Since several factors need to be taken into consideration before stopping a study, safety and study progress also will be taken into consideration by the DSMB

and Executive Committee in the decision to stop the study if an efficacy or futility boundary is crossed.

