13. APPENDIX A

The below graphs are based on simulation studies under various effect sizes (10,000 trials per effect size with a sample size of 1000 for each trial). The graphs illustrate the percentage of trials stopped at each interim look broken down by rejection of the alternative (futility) in red and rejection of the null (efficacy) in blue. For example, graph 1 shows the percentage of trials stopped when the effect size is the assumed alternative of 0.07. Blue represents stopping for overwhelming efficacy. Approximately 12% of the trials stop at the 1st look which coincides with our conservative stopping boundaries. Roughly 11% stop for overwhelming efficacy and ~1% stop for futility. Cumulative, we can see that ~66% of the trials stop prior to the final look. Overall, our rejection rate of the null is 81% and our rejection of the alternative (claiming futility) is 18.8% (which is our type II error for scenario 1).

Graph 4 illustrates the rejection rates under the null hypothesis of no effect. About 4% of the trials stop at the 1st look and 75% stop prior to the final look. Overall our rejection of the null is 4.8% (type I error under scenario 4). The other two scenarios illustrate the rejection rates when the effect size is somewhere between the null and alternative – 60% of the time we will stop early if the effect size is 0.03 and ~50% when the effect size is 0.05.

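### The SAP section defining the final primary test gives an unqualified 0.05, while the boundary table requires Z of 2.02 (p = 0.043) at that look

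*SAP*

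**What the plan says.** SAP 10.1.2 (Primary Efficacy Analysis at the End of the Trial) specifies a generalized linear model with treatment, NIHSS strata and thrombolysis use. It says that a Wald "chi-square test will be performed to compare the treatment group proportions using a two-tailed significance level of 0.05", with relative risks reported with 95% confidence intervals. Protocol 12.2.3 has the same sentence: "A Wald chi-square test will be performed to compare the treatment group proportions using a two-tailed significance level of 0.05".

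SAP 10.1.3 plans four interim looks and "one final look for a total of 5 planned analyses of the primary outcome". Boundaries come from gamma-family spending with gamma = -4, and futility is non-binding. The Final row of its table (1400 subjects) gives 2.02 (0.043) as the minimum statistic to reject the null.

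On error control, SAP 10.1.3 says that "under the null hypothesis of no difference the overall probability of crossing either outer boundary does not exceed the overall type I error rate". SAP 4.2 says that re-estimation is combined with the group sequential design "while preserving the overall type I error rate". Neither section gives that overall rate a number. Appendix A reports a simulated type I error of 4.8%.

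The cross-references do not settle which threshold governs. SAP 8 sends the analyst to 10.1.2 when imputed data sets are analysed at the interim and final analyses. SAP 4.1 cites Section 10.1.4 for the interim plan, which stands in 10.1.3. Protocol 12.2.1 defers to the SAP: "Details of all planned statistical analyses including the interim analyses will be provided in the study SAP".

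**The concern.** The section that defines the final primary test states a level without saying whether it is the overall level or the level for that look. The table in the next section gives a different threshold for the same test. A final p between 0.043 and 0.05 would be a positive trial under 10.1.2 as written and a negative one under the table. The four interim looks have already used part of the error, so a further test at 0.05 cannot keep the overall rate at 0.05. The decision rule of the only primary hypothesis should not have to be inferred after unblinding.

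**Working it through.** **Inputs from the documents.** Looks at 500, 700, 900, 1100 and 1400 subjects; gamma = -4; printed efficacy boundaries 2.97, 2.86, 2.65, 2.42, 2.02; printed interim futility boundaries 0.06, 0.13, 0.45, 1.05, non-binding (SAP 10.1.3). Rates 25% and 32% (SAP 4.1). 700 per arm follows from 1400 at 1:1. Method: recursive numerical integration with independent increments and a normal approximation.

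**1. Reproduce the table.** With overall two-sided level a = 0.05, the error spent by information fraction t is

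a(t) = 0.05 × (1 − e^(4t)) / (1 − e^4)

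- t = 500/1400 = 0.357: 0.05 × 3.173/53.598 = 0.0030, so Z = 2.97, as printed.
- t = 1100/1400 = 0.786: 0.05 × 22.170/53.598 = 0.0207 spent before the final look.

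| Look | Computed Z | Nominal p | SAP table |
|---|---|---|---|
| 500 | 2.972 | 0.0030 | 2.97 (0.003) |
| 700 | 2.859 | 0.0042 | 2.86 (0.004) |
| 900 | 2.648 | 0.0081 | 2.65 (0.008) |
| 1100 | 2.418 | 0.0156 | 2.42 (0.016) |
| 1400 | 2.0235 | 0.0430 | 2.02 (0.043) |

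The printed boundaries also reproduce the chance of stopping before the final look under the null (0.750; SAP 0.75). The table is therefore built on an overall two-sided 0.05.

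**2. Change only the final critical value.**

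| Final criterion | Overall alpha, futility non-binding | Overall alpha, futility obeyed |
|---|---|---|
| Z ≥ 2.02 (table) | 0.0503 | 0.0483 |
| Z ≥ 1.96 (10.1.2 read literally) | 0.0562 | 0.0535 |

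The excess over 0.05 in the 0.0503 comes from rounding the printed boundaries. Appendix A's 4.8% matches 0.0483 and not 0.0535. Because futility is non-binding, the middle column is the relevant one for type I error.

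**3. How often the zone 1.96 ≤ |Z| < 2.02 decides the trial** (control 25%, futility obeyed):

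| True insulin rate | All trials | Trials reaching the final look |
|---|---|---|
| 25% | 0.5% | 2.1% |
| 28% | 1.5% | 3.6% |
| 30% | 1.9% | 4.1% |
| 32% | 1.2% | 3.6% |

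Power at 25% against 32% is 0.809 with 2.02 and 0.822 with 1.96. The plan's 80% therefore does not depend on the looser threshold.

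**4. Worked example, unadjusted.** Control 175/700, log relative risk Wald test, SE = √(1/x − 1/700 + 1/175 − 1/700):

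- x = 207: Z = 0.1679/0.0877 = 1.915, p = 0.0555. Negative under both.
- x = 208: Z = 0.1728/0.0875 = 1.973, p = 0.0485. Positive under 10.1.2, negative under the table.
- x = 209: Z = 0.1775/0.0874 = 2.031, p = 0.0423. Positive under both.

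At x = 208 the 95% interval for the relative risk is exp(0.17275 ± 1.96 × 0.08755), or 1.001 to 1.411. It excludes 1 although the tabulated boundary is not crossed.

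**5. Check with the planned covariates.** A null simulation (300,000 trials per allocation, log-link model with NIHSS strata and thrombolysis) gave 0.0494–0.0496 with 2.02 and 0.0553–0.0555 with 1.96, futility non-binding. With futility obeyed it gave 0.0475–0.0478 and 0.0528–0.0531. Its assumptions are not in the documents: NIHSS mix 45/33/22%; thrombolysis 60%; favorable rates about 21% without and 27–28% with thrombolysis; and 1:1, 60:40 or 40:60 allocation after the first look as a stand-in for response-adaptive randomization.

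**The case against.** The best reply is that nothing is really in conflict. Section 10.1.3 directly follows 10.1.2 under the same heading, its Final row is explicit, and Appendix A fits only that row. No number other than 0.05 is offered as the overall rate, so 0.05 in 10.1.2 is naturally that rate. On that reading there is no conflict and no inflation. Naming the overall level in the test section is also reasonable, because 0.043 holds only for the planned look times, and both the looks and the sample size may change.

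Much of this stands. The overall reading is very probably the intended one, the design is sound, and the effect of a misreading is small. The covariate simulation adds no documentary support, only a check that the gap persists under assumed inputs. But the intent has to be recovered by reconstructing the table: no sentence in the SAP says it, and SAP 8 sends the analyst for the final analysis to the section with the unqualified level. That the bar can move is a reason to name the spending-function boundary in 10.1.2, not to leave it out.

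A fair drafting point also stands. Z = 2.02 gives p = 0.0434, and p = 0.043 needs Z of about 2.024, so a correction should name one governing criterion rather than treat the two rounded figures as identical.

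**Conclusion.** The concern holds as an unreconciled decision rule, not as an error in the boundaries, sample size or power. Followed literally, SAP 10.1.2 gives an overall two-sided type I error of 0.0562 instead of 0.0503 (0.0535 instead of 0.0483 with futility obeyed). It would change the conclusion in 0.5% of trials under the null and in at most 1.9% at the true differences examined. The closed-form figures assume 1:1 allocation, a normal approximation and the planned look times. Response-adaptive allocation itself was not modelled; fixed 60:40 and 40:60 splits left the gap unchanged. It should be fixed because it concerns the threshold for the sole primary claim, even though it would rarely matter.

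**What to change.** Add to SAP 10.1.2: the overall two-sided type I error is 0.05; the final Wald statistic is judged against the final-look boundary of Section 10.1.3, computed from the gamma(-4) spending function at the actual look times (as planned, |Z| of 2.02, nominal p 0.043; 2.0235 unrounded).

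Optionally, note that the reported 95% confidence interval is descriptive and is not the decision rule, and align Protocol 12.2.3 at the next amendment made for other reasons.

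The cost is one sentence. Sample size, boundaries and planned power stay as they are, because the bar remains the tabulated one. No protocol amendment, with its Executive Committee and IRB approvals (Protocol 15.2.2), is needed for this alone, because Protocol 12.2.1 leaves the details to the SAP.

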4. SAMPLE SIZE DETERMINATION FOR THE PRIMARY EFFICACY OBJECTIVE

4.1 Sample Size Estimation

The primary outcome variable is the overall proportion of subjects experiencing a favorable outcome 90-days post randomization, where favorable is defined by the dichotomized mRS score as adjusted to the baseline NIHSS (stroke severity). Our preliminary data suggest a 25% rate of favorable outcome in the control group at 90 days is reasonable. A clinically relevant absolute difference in success rates between the two interventions is chosen as 7% (success rate_{control}=25%; success rate_{infusion}=32%). If the IV insulin group does not have at least a 7% or higher success rate than the control group, then IV insulin within 12 hours of symptom onset will not be considered a worthwhile therapy for hyperglycemic acute ischemic stroke patients.

Based on the above information and taking into consideration four planned interim analyses (see Section 10.1.4 for details), the study is powered to assure 80% likelihood of identifying a difference in success rates greater than or equal to 7%. Sample size estimation is based on the comparison of independent proportions adjusting for baseline NIHSS. The maximum sample size required for randomization is 1314 subjects (657/treatment group). Although every attempt will be made to avoid drop outs and losses to follow up, the required sample size is inflated for a 3% non-adherence rate. The total number of patients required for randomization is 1400.

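### The SAP plans only an ordinary relative risk and 95% interval despite four efficacy looks, so the benefit reported after an early efficacy stop would be overstated

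*SAP*

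**What the plan says.** SAP 10.1.2, headed as the analysis at the end of the trial, fits a generalized linear model adjusted for NIHSS stratum and thrombolysis. A Wald "chi-square test will be performed to compare the treatment group proportions using a two-tailed significance level of 0.05". For the effect size it says only: "Adjusted relative risks will be reported with two-sided 95% confidence intervals". Protocol 12.2.3 has the same sentence. The adjustment is for covariates, not for interim stopping.

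SAP 10.1.3 says: "The study is designed using four interim looks for both efficacy and futility of the primary outcome". The looks are at 500, 700, 900 and 1100 subjects, with a final analysis at 1400. The efficacy boundaries are Z = 2.97, 2.86, 2.65, 2.42 and 2.02, the last with p = 0.043. SAP 10.1.3 and Appendix A deal with boundaries and stopping probabilities. Neither document mentions a repeated interval, a stagewise ordering or a bias-adjusted estimate.

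SAP 4.1 sets the relevance threshold on the absolute scale. "If the IV insulin group does not have at least a 7% or higher success rate than the control group", the therapy will not be considered worthwhile. The protocol's section on preliminary data adds that an effect of 4–6% was felt to be too small for a labor-intensive therapy.

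**The concern.** A trial that stops for efficacy does so because its estimate was high at that moment, so the ordinary estimate is biased upward among trials that stop. The error-spending boundaries protect the type I error of the test. They do nothing for the estimate or the interval reported with it.

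Here an early stop is the likelier course if the design effect is true, and the sponsor has named an absolute gain below which the treatment is not worth its effort. A true gain of 3 to 5 points, below that mark, could be published as 9 points. Guidance for a labor-intensive treatment would rest on that figure. A correction chosen after a favourable result is known would also carry less weight than one written down beforehand.

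**Working it through.** **Inputs.** Control rate 25%, alternative 32% (SAP 4.1). Looks, efficacy boundaries and inner futility wedge (SAP 10.1.3; wedge 0.06, 0.13, 0.45, 1.05). Accrual 33.3 per month (SAP 10.1.3). Assumptions: 1:1 allocation, an unadjusted pooled Z in place of the covariate-adjusted Wald test, and futility stops followed.

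**Step 1: reproduce the plan.** Two-sided 0.05 gamma(−4) spending at n/1400, with non-binding futility, returns 2.97, 2.86, 2.65, 2.42 and 2.02. In 400,000 simulated binomial trials at 25% against 32%, the probabilities of crossing either boundary are 0.116, 0.130, 0.190, 0.221 and 0.343 (SAP: 0.12, 0.13, 0.19, 0.22, 0.34). Rejection is 80.9% (SAP: 81%). Under no effect, 4.8% reject and 75% stop early, as the SAP states. The 66% that stop before the final look under the alternative include futility stops; efficacy stops alone are 58%.

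**Step 2: observed gain needed to cross.** Solve d = c × √[4p(1−p)/n], with p = 0.25 + d/2. At look 1, p = 0.3115, so d = 2.97 × √(4 × 0.3115 × 0.6885/500) = 2.97 × 0.0414 = 0.123.

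| Look | n | c | Gain needed, 25% control | Range, control 20–35% |
|---|---|---|---|---|
| 1 | 500 | 2.97 | 12.3 points | 11.6–13.1 |
| 2 | 700 | 2.86 | 9.9 | 9.3–10.6 |
| 3 | 900 | 2.65 | 8.0 | 7.5–8.6 |
| 4 | 1100 | 2.42 | 6.6 | 6.2–7.1 |
| Final | 1400 | 2.02 | 4.8 | not needed here |

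**Step 3: the ordinary estimate, given an early stop in favour of IV insulin.** Coverage is for the ordinary 95% interval for the relative risk.

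| True gain (points) | Chance of early efficacy stop | Mean observed gain | Observed gain ≥ 7 | Same, with 100 overrunning subjects | Coverage |
|---|---|---|---|---|---|
| 7 | 58% | 9.9 | 92% | 89% | about 95% |
| 5 | 31% | 9.2 | 85% | 80% | 89% |
| 4 | 19% | 9.0 | 82% | 75% | 79% |
| 3 | 11% | 8.8 | 78% | 69% | about 62% |

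The overrun is 3 months × 33.3 = about 100 subjects still in follow-up at the look. The mean observed relative risk after such a stop is 1.40 to 1.43 in every row, against true values from 1.12 (0.28/0.25) to 1.28 (0.32/0.25). Look 4 supplies 32%, 41% and 46% of these stops for true gains of 7, 5 and 3. There the observed gain reaches 7 points in 75%, 64% and 52%. An assumed 60:40 allocation after look 1, standing in for the response-adaptive scheme, changes the share at or above 7 points by about one point or less.

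**Step 4: over all trials.** Coverage of the ordinary interval is 93–95%. The mean observed gain is 7.7, 5.2 and 2.8 for true gains of 7, 5 and 3.

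**Step 5: repeated intervals.** The interval is estimate ± c × SE, on the log scale for the relative risk. For a result exactly on the look 1 boundary, RR = 0.373/0.25 = 1.49 and SE = √(1/93.25 − 1/250 + 1/62.5 − 1/250) = 0.137. The ordinary interval is exp(0.400 ± 1.96 × 0.137) = 1.14–1.95. The repeated interval uses 2.97 and gives 0.99–2.24. At looks 2, 3 and 4 the ordinary intervals 1.11–1.76, 1.07–1.63 and 1.04–1.53 become 1.00–1.96, 1.00–1.75 and 1.00–1.60. For true gains of 3 to 7, repeated intervals for the relative risk cover the truth in at least 98% of early efficacy stops (97% with overrun).

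**Step 6: median-unbiased estimate under stagewise ordering.** For a Z that is 0.5 above the boundary, the ordinary gains of 14.0, 11.5, 9.5 and 7.95 points at looks 1 to 4 become 14.0, 10.9, 8.9 and 7.4.

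**Step 7: the final look.** A final Z between 1.96 and 2.02 would be significant under the 0.05 test in SAP 10.1.2 and its 95% interval would exclude 1, yet it would not cross the boundary in SAP 10.1.3.

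**The case against.** A reader might infer three stronger points, and the documents do not support them.

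- That an early efficacy stop all but guarantees an observed gain above 7 points. This is so at looks 1 to 3 (at a 25% control rate). The look 4 boundary is about 6.6 points, and look 4 supplies 32–46% of the early efficacy stops for true gains of 3 to 7.
- That the planned interval is generally unreliable. Its coverage over all trials is 93–95%, and about 95% after an early efficacy stop if the true gain is 7. The shortfall appears when the truth is well below 7, where early efficacy stops are uncommon. At a true gain of 3 or 4, an early efficacy stop together with an interval that misses the truth occurs in about 4% of trials.
- That an observed 7 points is a decision rule. SAP 4.1 uses the figure to justify the effect size and does not say observed. The hypothesis in SAP 10.1.1 is a zero coefficient, and the final boundary corresponds to about 4.8 observed points.

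It is also fair to say that use of the ordinary estimate after an early stop is inferred from silence under an end-of-trial heading, that the boundaries are conservative, and that the DSMB and the Executive Committee weigh safety and study progress before stopping. The first of these is the gap itself, since no other estimator is given. The others do not remove the bias in trials that do stop.

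The correction has limits too. At a true gain of 4, the stagewise estimate lowers the mean after an early efficacy stop only from 9.0 to 8.7 points, and the share at or above 7 only from 82% to 76%.

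**Conclusion.** The gap is real, and it concerns reporting; it does not touch the validity of the test. The plan has four efficacy looks and no method of estimation suited to them. After an early efficacy stop the ordinary estimate would on average overstate a true 7-point gain by about 3 points (9.9 − 7) and a true 3-point gain by about 6 (8.8 − 3). The ordinary interval falls clearly below its nominal coverage when the true gain is 5 points or less. Of early efficacy stops, 78–92% show at least 7 points for true gains of 3 to 7, or about 69–89% with overrun. The comparison with the 7-point threshold is therefore uninformative at looks 1 to 3 and somewhat more informative at look 4. Separately, the 0.05 test and 95% interval do not match the final boundary of Z = 2.02.

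These sizes rest on a 25% control rate, 1:1 allocation, the printed boundaries, futility stops being followed, and an unadjusted statistic standing in for the adjusted Wald test.

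**What to change.** Add a paragraph to SAP 10.1.2, and point to it from protocol 12.2.3:

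- Report the adjusted relative risk and the risk difference with repeated confidence intervals, estimate ± c × SE (log scale for the relative risk). Here c is the critical value from the spending function at the look actually used: 2.97, 2.86, 2.65, 2.42 or 2.02 if the looks fall as planned, and recalculated if the DSMB changes their timing. This also aligns the final interval with the final boundary.
- State that the interval uses the model and scale of the monitored test statistic. Otherwise a result on the boundary can give an interval that just includes 1, as at look 1 in step 5.
- After an early efficacy stop, add a named bias-adjusted estimate, for example the median-unbiased estimate under stagewise ordering. Note that its correction is modest, and nil at look 1.
- Show the ordinary estimate and 95% interval beside these, labelled as not adjusted for early stopping.
- Do not add a decision rule based on an observed 7 points.

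The cost is a paragraph and a few lines of programming. Boundaries, sample size and trial conduct stay as they are. The downside is wider, conservative intervals: at look 1 the half-width on the log scale grows by 2.97/1.96, about 1.5 times, and at the final look by 2.02/1.96, about 3%.
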